8. STUDY PARTICIPANTS AND DEMOGRAPHICS

8.1 Disposition of Participants and Withdrawals

The numbers and percentage of participants entering, completing the study, and withdrawing from the study, along with reasons for withdrawal, will be tabulated overall and by treatment group. This summary will be based on all participants who have data entered into the database.

8.2 Protocol Deviations

Protocol deviations will be checked on complete data for all participants, determined during a data review meeting before database lock and the final analysis.

Protocol deviations will be summarized by type and by treatment group for the Safety population. Protocol "violations" are not differentiated from deviations; instead, each deviation is identified either as "major" or "minor" depending upon its potential impact upon the integrity of the study data or the participant's well-being.

Individual participants with protocol deviations will be listed.

Protocol: TNX-CY-P306 Page 18 of 36

Final v1.0

8.3 Demographics and Other Baseline Characteristics

Descriptive summaries of the demographic and other baseline characteristics will be completed for all participants in the safety population by treatment groups, unless otherwise specified.

Descriptive summaries of demographic and other baseline conditions will include:

- Demographics (age, gender, race/ethnicity, height, weight, body mass index (BMI), family status, education, presence of current MDE, current nicotine, alcohol and THC usage, and employment status).
- CAPS-5 Assessment (Diagnostic version)

Other assessment's baseline values will be reported with their respective follow-up measures.

Medical History will be coded using Medical Dictionary for Regulatory Activities (MedDRA) version 19.0 and summarized by System Organ Class (SOC) and Preferred Term using frequency counts by treatment group. Note that the medical history, demographics, and baseline characteristic data are collected in the lead-in study; this analysis displays that information for the population of subjects that entered this study.

Protocol: TNX-CY-P306 Page 19 of 36

Final v1.0

9. EFFICACY ANALYSES

9.1 Continuous Outcomes

The mean change from baseline in the continuous outcome of interest will be analyzed using a restricted maximum likelihood (REML) based repeated measures approach, without imputation. The model will include all participants in the safety population. The dependent variable will be the observed change from baseline with respect to each outcome at each post-randomization visit.

9.1.1 Efficacy Analysis Model

A Mixed Model Repeated Measures (MMRM) analysis will be performed for the change from baseline in separate, independent models for each endpoint. The model will include all participants in the safety population, and the dependent variable will be the observed change from baseline the outcome of interest at each post-randomization visit. Covariates in the model will include the fixed categorical effects of treatment group exposure, site, sex, visit and treatment group by visit interaction, as well as the continuous fixed covariates of baseline score and baseline score by visit interaction. An unstructured covariance matrix will be used to model the within-subject variance-covariance errors. The Kenward-Roger approximation will be used to estimate the denominator degrees of freedom. Should the unstructured model fail to converge, an autoregressive AR(1) covariance structure will be attempted, then finally compound symmetric should AR(1) not converge.

The least squares means and 95% confidence intervals (CIs) will be calculated for the treatment difference between the subjects that received TNX-102 SL in a prior study and those that did not.

These endpoints to be analyzed with this model will include:

- CGI-I score.
- Change from baseline in SDS total.
- Change from baseline in participants' quality of sleep using the PROMIS Sleep Disturbance scale.
- Change from baseline in the disruption of work/school activities assessed using the SDS.
- Change from baseline in disruption of social life/ leisure activities assessed using the SDS.
- Change from baseline in the disruption of family life/home responsibilities assessed using the SDS.
- Change from baseline in BDI-II score.

The model will be changed to include the corresponding baseline value of each the endpoints. To estimate the difference between the treatment arms in CGI-I score (which does not have baseline assessments), the same method will be used, however, with the observed baseline response and associated interactions removed from the list of covariates. All visits will be included in the analysis. P-values from these comparisons will be considered nominal.

Protocol: TNX-CY-P306 Page 20 of 36

Final v1.0

For each outcome, descriptive statistics (mean, SD, median, minimum and maximum) will be reported as well as LS means, standard error (SE) and p-values comparing the arms at each visit. In addition, for the SDS, the frequency of participants not working or attending school due to reasons unrelated to PTSD will be reported overall and within each visit.

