# 12.2. Evaluation of Efficacy

As this is a long-term safety study, minimal conclusions will be available concerning long-term efficacy. The efficacy analyses will focus on durability of the response achieved prior to entry into this extension study, based on the CGI-I for patients in Track A and for patients on active drug in the lead-in HONOR study or the P303-early-terminated patients (due to IA results) who were on placebo in P301 in Track B. In addition, durability of response for both Track A and B patients will be assessed by measuring the change in PCL-S scores from Visit 5 (Week 28) to Visit 6 (Week 40) in order to detect any potential worsening in PTSD symptoms as a result of longer term use of TNX-102 SL 5.6 mg. For Track B patients, an additional Visit 7 (Week 52) PCL-S assessment with be available for subset analysis of durability of response.

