2.2 Study Endpoints

2.2.1 Efficacy Endpoints

Comparisons will be made at each study week of data collection to the baseline of this study.

Efficacy endpoints include:

- Average CGI-I score (scored 1-7)
- Proportion of patients with a CGI-I score of "very much improved" or "much improved"
- Change from baseline in the SDS total score
- Change from baseline in the individual items assessed using the SDS
- Change from baseline in patients' quality of sleep using the PROMIS Sleep Disturbance scale
- Change from baseline in BDI-II score
- Change from week 28 to week 40 in PCL-S
- Change from week 28 to week 52 in PCL-S (Track B subjects only)
- Change from week 40 to week 52 in PCL-S (Track B subjects only)

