3.2 Method of Treatment Assignment and Randomization

All patients will be assigned to TNX-102 SL, 5.6 mg regardless of which treatment arm they were randomized to in the lead-in study. No patients or site personnel will know what the prior treatment was in the double-blind lead-in study.

Throughout this document, when describing analyses performed by treatment group, this will refer to the treatment that the subject was randomized to in the double-blind lead-in study.

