9.1.2 Categorical outcomes

The proportion of responders (participants with a CGI-I score of "much improved" or "very much improved") over time will be reported with the number and percentage of participants in each group (participants that received TNX-102 SL in a prior study and those that did not). Participants with missing data will be analyzed as though they are non-responders. A difference in proportions Z-test and the corresponding two-sided 95% CIs will also be reported. Two-sided p-values for the test of no difference between the groups will be provided.

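### The efficacy p-values and confidence intervals compare patients with and without prior TNX-102 SL rather than testing change from P306 baseline, so the formal inference does not address durability

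*SAP*

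**What the plan says.** On the question to be answered:

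- SAP 2.2.1: "Comparisons will be made at each study week of data collection to the baseline of this study".
- Protocol 12.2: "The efficacy analyses will focus on durability of the response achieved prior to entry into this extension study, based on the CGI-I". It adds a second durability measure, PCL-S change from Week 28 to Week 40, with Week 52 for Track B.

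On treatment in P306, SAP 3.2: "All patients will be assigned to TNX-102 SL, 5.6 mg regardless of which treatment arm they were randomized to in the lead-in study".

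On the inference:

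- SAP 9.1.1 models change from baseline by MMRM. It says LS means and 95% CIs will be "calculated for the treatment difference between the subjects that received TNX-102 SL in a prior study and those that did not". Each outcome also gets descriptive statistics "as well as LS means, standard error (SE) and p-values comparing the arms at each visit".
- SAP 9.1.2 reports the number and percentage of CGI-I responders in each group, then a Z-test and CI for the difference: "Two-sided p-values for the test of no difference between the groups will be provided".
- The PCL-S changes are endpoints in SAP 2.2.1 but are missing from the list of modelled endpoints in 9.1.1.
- SAP 10.2 and 10.4 do give 95% CIs for change from baseline, but only for laboratory values and vital signs.
- SAP 7.1.1 makes all p-values nominal.

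**The concern.** Durability is a question about each group's own course: has the mean moved from where it stood at P306 entry? The planned contrast asks whether two groups, both now on the drug, move by different amounts. That is a legitimate question about prior exposure, but a different one.

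Its sign is also hard to read. If the drug works, patients new to it may improve more than patients who already have the benefit, so a difference favouring the group without prior TNX-102 SL is compatible with full durability in the other group.

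What is at stake is how the secondary objective is interpreted. A non-significant contrast could be taken as sustained effect when everyone has worsened. A significant one could be taken as lost durability when prior-TNX patients have not changed.

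**Working it through.** **1. The two questions side by side.** Let A be the mean change from P306 baseline in prior-TNX patients and B the mean change in the others. The stated comparison concerns A = 0 and B = 0. The planned test concerns A − B = 0. Neither implies the other.

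**2. Inputs.** The plan has no figure to reproduce: SAP 5 and protocol 12.3 state that no sample size calculation was made, and protocol 6.2 gives only a cap of 200. Two-sided alpha is taken as 0.05. Total N of 50, 100 or 200, the group splits, and shifts of 0.2, 0.3 and 0.5 SD of change are all assumptions.

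**3. Both groups worsen by the same amount L.**

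- Planned contrast: rejection = Φ(|d|/√(1/n1 + 1/n2) − 1.96) + Φ(−|d|/√(1/n1 + 1/n2) − 1.96). Here d = 0, so rejection = 2Φ(−1.96) = 5% at any size or split.
- Test of overall change against baseline: Φ(L√N − 1.96) plus a negligible second tail. For L = 0.3 and N = 100, 3.00 − 1.96 = 1.04 and Φ = 85%.

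| Total N | Planned contrast | Against baseline, L = 0.2 | L = 0.3 | L = 0.5 |
|---|---|---|---|---|
| 200 | 5% | 81% | 99% | 100% |
| 100 | 5% | 52% | 85% | 99.9% |
| 50 | 5% | 29% | 56% | 94% |

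**4. Prior-TNX patients unchanged, the others improve by d.** The same between-group formula applies. For d = 0.5 with 50 per group, 0.5/√(1/50 + 1/50) = 2.5, 2.5 − 1.96 = 0.54, and Φ = 71%.

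| Groups | d = 0.2 | d = 0.3 | d = 0.5 |
|---|---|---|---|
| 100/100 | 29% | 56% | 94% |
| 134/66 | 27% | 51% | 91% |
| 50/50 | 17% | 32% | 71% |
| 25/25 | 11% | 19% | 42% |

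**5. Baseline-adjusted check.** A single-visit ANCOVA of change on group and baseline was simulated (4,000 runs, complete data, assumed correlation 0.6, shifts in baseline SD).

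- Both groups worsen by 0.5: the contrast rejects 5.1% (100/100), 5.0% (133/67) and 4.9% (50/50). A test against baseline rejects 100%.
- Prior-TNX unchanged, others improve by 0.5: 99% (100/100), 86% (50/50), 57% (25/25). With 0.3: 75% (100/100). These exceed step 4 because the residual SD is √(1 − 0.36) = 0.8 baseline SD, so 0.5 becomes 0.5/0.8 = 0.625 residual SD.
- Both groups unchanged, equal baselines: 4.8%, the nominal rate.
- Both groups unchanged, baseline means 0.3 or 0.5 apart: the adjusted contrast is off by (1 − 0.6) × 0.3 = 0.12 or (1 − 0.6) × 0.5 = 0.20, and rejects 18% or 40% (100/100).

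**6. Responder test.** SAP 7.2.1 anchors CGI-I at the start of P306 with 4 meaning no change, so a patient who fully holds an earlier response scores 4 and counts as a non-responder. With assumed responder rates of 10% in a maintained group and 30% in the other, the Z-test rejects 95% (100/100) or 71% (50/50).

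**7. Which groups?** SAP 3.2 defines treatment group by randomised lead-in arm. SAP 9.1.1 and 9.1.2 describe the contrast by receipt of TNX-102 SL in a prior study. A patient on placebo in P301 who then took TNX-102 SL in P303 is in the placebo group under 3.2 and in the prior-TNX group under section 9. The protocol synopsis places such patients, if active in P303 when it was discontinued, in Track B, and protocol 12.2 counts them in its durability analysis.

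**The case against.** The case for leaving the plan alone is substantial. Safety is the primary objective. Protocol 6.3.2 promises only descriptive efficacy statistics, and 12.2 warns that few efficacy conclusions will be possible. SAP 2.2.1 names a comparison, not a hypothesis test. P-values are nominal and SAP 7.2 sets no testing order. Nothing in the documents says that a non-significant contrast will be read as durability. A test that rejects 5% of the time when its own null is true is behaving correctly. Within-group change is uncontrolled, so an interval that excludes zero cannot be attributed to the drug.

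All of this stands, and it limits the seriousness of the point. It does not remove the mismatch. SAP 9 goes beyond description to p-values and CIs, and all of them address the contrast that the stated focus does not ask about. The general line in SAP 7.1 attaching 95% CIs to statistical tests does not help, because the only efficacy tests are between groups.

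Two stronger readings are tempting, and the documents support neither:

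- A reader might infer that a shared loss would be hidden. It would not: change from P306 baseline is the modelled variable, and per-arm descriptive statistics, LS means and SEs are planned at each visit. An approximate interval (LS mean ± 1.96 SE) could be formed from them.
- A reader might infer that the tests reject whenever response is perfectly maintained. If both groups hold from equal baselines, they reject at the nominal rate. Excess rejection requires the other group to change, or baseline means to differ under the adjusted model.

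**Conclusion.** The point holds as a mismatch between the stated efficacy question and the formal inference. Against a loss shared equally by both groups, the planned contrast has power equal to alpha. This follows from its null being true and needs no assumption about sample size, split or correlation. The other rates (for example 71% rejection at 50/50 when only the patients without prior TNX-102 SL improve, by 0.5 SD of change) rest on assumed sizes, splits, effects and correlation, with one visit and no dropout, and show scale only.

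What is missing is an interval on an estimate already planned, together with a statement of what the between-group contrast can and cannot show. For a nominal, secondary analysis this should be corrected; it does not threaten the primary safety objective. The unresolved group definition adds to it, since it changes who is counted as already exposed.

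**What to change.** 1. In SAP 9.1.1, report LS-mean change from P306 baseline at each visit with its 95% CI, by prior-exposure group and overall, from the MMRM already planned. State how the groups are weighted in the overall estimate.
2. Report CGI-I as LS mean minus 4 with its 95% CI, so that zero means no change since P306 entry.
3. Add PCL-S to section 9 as change from Week 28 with its 95% CI.
4. In SAP 9.1.2, give each group's responder proportion with its 95% CI, noting that a fully maintained patient scores as a non-responder.
5. Keep the between-group difference and Z-test, labelled exploratory. State that a non-significant value is not evidence of maintained response.
6. Reconcile SAP 3.2 with 9.1.1 and 9.1.2 on the group definition, and say where P301-placebo patients who took TNX-102 SL in P303 belong.

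The cost is wording and a few extra contrast statements; no new data are needed. If the analysis has already been run, the additions can be reported as post hoc, as SAP 1 requires.

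There are two downsides. Within-group changes are uncontrolled and open-label, and other PTSD therapies are allowed (protocol 8.5), so they must be labelled as such. The model-based interval is also slightly narrow because it treats the sample baseline mean as fixed: under no change, the simulated prior-TNX LS-mean test rejected 6–7% rather than 5%.

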## 9.1.2. Screening Overview

The first study visit, Visit 1, will be where the study is explained to the prospective study patient, where written informed consent will be obtained and documented, and where protocol-specified study procedures and assessments will be completed.

For patients enrolling into this study from the 12-week open label extension study, P303, the P306 Baseline Visit (Visit 1) date is intended to be the same date as the final visit of the 12-week open label extension study, P303. However, if there are extenuating circumstances, Visit 1 of P306 may occur within fourteen days of their final visit in P303 without repeating baseline assessments. If more than fourteen days elapse between the final visit of P303 and start of the P306 study, medical monitor approval will be required and baseline assessments will need to be repeated.

For patients enrolling directly from the double-blind lead-in study, P301, all Visit 1 assessments will be performed. These patients are also expected to enter the P306 study at the same time as their final P301 visit; however, if there are extenuating circumstances, then Visit 1 of P306 may occur within fourteen days of their final P301 visit.

Once the patient has provided written informed consent to participate and has met all relevant inclusion criteria, this patient is eligible to begin the open-label treatment period, starting at bedtime on the day of enrollment. The patient should be dispensed three bottles of TNX-102 SL tablets, along with dosing and storage instructions. The end-of-study information collected at the final visit of the 12-week open label extension study P303, or the Visit 1 assessments completed as part of this protocol, will be considered the baseline values for Study P306.

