7.2 Efficacy Assessments

There is no formal testing order to the efficacy assessments in this protocol; however, they are described below in approximate order of importance.

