7.2.1 Clinician Global Impression of Improvement (CGI-I)

The CGI-I will be completed by an Investigator to evaluate the participant's status since the start of the current study (P306). The CGI-I will be completed at each in-clinic visit after baseline. It will be the responsibility of the Principal Investigator or his qualified designee to assess change in the subject's overall status and answer the following question:

Since the initiation of treatment in P306, the participant is:

- 1 = Very much improved
- 2 = Much improved
- 3 = Minimally improved
- 4 =No change
- 5 = Minimally worse
- 6 = Much worse
- 7 =Very much worse

The primary analysis of CGI will treat it as a continuous variable (scored 1-7 as above). There will be an additional outcome presented where a responder on the CGI-I is defined a participant who is scored as 'Very much improved' or 'Much improved' and compared between the study arms.

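### The CGI-I model loses its baseline term without a substitute and the responder test is unadjusted; adding a severity score already collected would be a cheap improvement, not the repair of an error

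*SAP*

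**What the plan says.** SAP 9.1.1 fits a separate MMRM to each continuous efficacy endpoint. The shared terms are "fixed categorical effects of treatment group exposure, site, sex, visit and treatment group by visit interaction", plus the endpoint's own baseline score and its interaction with visit. CGI-I is the exception: "To estimate the difference between the treatment arms in CGI-I score (which does not have baseline assessments), the same method will be used", but "with the observed baseline response and associated interactions removed from the list of covariates". No other severity measure is named, so what remains is group, site, sex, visit and group by visit.

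For CGI-I responders, SAP 9.1.2 counts missing data as non-response and then states: "A difference in proportions Z-test and the corresponding two-sided 95% CIs will also be reported". There are no covariates and no strata.

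On the standing of these analyses, SAP 7.2.1 says "The primary analysis of CGI will treat it as a continuous variable" and makes the responder rate an additional outcome. SAP 7.2 says "There is no formal testing order to the efficacy assessments in this protocol; however, they are described below in approximate order of importance", and CGI-I is the first one described.

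On available baselines, SAP 7.2.2 and 7.2.3 place SDS and PROMIS at baseline and BDI-II at all in-clinic visits. Protocol 9.1.2 says that the final P303 visit data, or the P306 Visit 1 assessments, "will be considered the baseline values for Study P306".

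**The concern.** All patients receive the same drug in P306. The comparison is by prior treatment (SAP 3.2 and 9.1.1), among patients who chose to continue and met the entry criteria on compliance and on worsening of depression or suicidality (Protocol 7.2). Their P306 baseline is taken after lead-in treatment and, for some, after P303 treatment. The synopsis also ties Track A to prior active drug, so route of entry and time on drug differ by group. Lead-in randomisation therefore does not assure equal severity at P306 entry.

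CGI-I is rated against that entry state (SAP 7.2.1). A patient who enters with few symptoms has little room to be rated much or very much improved. If the groups enter at different severity, part of any CGI-I difference may reflect entry severity rather than prior exposure. If severity predicts CGI-I at all, leaving it out also widens the interval. The other modelled endpoints have this adjustment; CGI-I, the one described first, does not.

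**Working it through.** **Inputs from the documents.** Enrolment is up to 200 (Protocol 6.2), with no group split. There is no sample-size calculation (SAP 5) and no efficacy effect size, SD or correlation. There is thus no planned figure to reproduce, and everything below is illustration.

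**Assumed inputs.** rho is the absolute correlation of entry severity with CGI-I, taken as 0.1, 0.3 and 0.5. Because site and sex are already in the model, it should be read as a partial correlation. d is the standardised entry-severity gap between groups, taken as 0.2 and 0.4. Groups are taken as 100 each. The calculation is for a single visit.

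**Precision.** SE(adjusted) / SE(unadjusted) = sqrt(1 − rho²). An unadjusted analysis of 200 patients is worth an adjusted analysis of 200 × (1 − rho²).

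| rho | SE ratio | SE cut | Equivalent N |
|---|---|---|---|
| 0.1 | sqrt(0.99) = 0.995 | 0.5% | 198 |
| 0.3 | sqrt(0.91) = 0.954 | 4.6% | 182 |
| 0.5 | sqrt(0.75) = 0.866 | 13.4% | 150 |

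**Imbalance, CGI-I score.** The unadjusted contrast moves by rho × d in CGI-I SD units, in a direction that the documents do not settle. With 100 per group the standard error is sqrt(2/100) = 0.141 SD. If there is no difference at equal entry severity, the nominal 5% two-sided rejection rate becomes 1 − Φ(1.96 − k) + Φ(−1.96 − k), where k = rho × d / 0.141.

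| rho | d | Shift (SD) | Rejection rate |
|---|---|---|---|
| 0.1 | 0.2 | 0.02 | 5.2% |
| 0.1 | 0.4 | 0.04 | 5.9% |
| 0.3 | 0.2 | 0.06 | 7.1% |
| 0.3 | 0.4 | 0.12 | 13.6% |
| 0.5 | 0.2 | 0.10 | 10.9% |
| 0.5 | 0.4 | 0.20 | 29.3% |

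**Imbalance, responders.** With a latent normal response and a rate near 50%, the shift is Φ(rho × d/2) − Φ(−rho × d/2). At rho 0.3 it is 2.4 percentage points for d = 0.2 and 4.8 for d = 0.4. At rho 0.5 and d = 0.4 it is 8.0.

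**Model size.** There are five post-baseline in-clinic visits (Weeks 7, 16, 28, 40 and, for Track B, 52). One score with its visit interaction adds 5 slopes; two scores add 10. The model already carries about 35 sites for at most 200 patients, which favours one score.

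**The case against.** The strongest reply is that nothing in the plan is broken. CGI-I is itself a rating of change and has no baseline, and SAP 9.1.1 gives that as the reason for removing the term. Using another scale as a surrogate is a choice, not a correction. This stands. It explains why CGI-I's own baseline is absent, though, not why no related score is used. SDS, PROMIS and BDI-II are also analysed as change and still carry a baseline.

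Second, little depends on the result. P-values are nominal (SAP 7.1.1), the protocol plans descriptive efficacy statistics (6.3.2), and it expects only minimal efficacy conclusions, with a focus on durability of response (12.2). The wholly unadjusted Z-test serves only the additional outcome, and the CGI-I MMRM keeps site and sex. All of this stands and keeps the point small. The SAP nevertheless commits to between-group estimates, intervals and p-values.

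Third, a reader might infer that the planned CGI-I contrast is biased. The documents do not support that. Entry severity is measured after lead-in treatment, so in previously exposed patients it may partly be an effect of TNX-102 SL. Conditioning on it answers a different question: the difference between groups at equal entry severity. The SAP already accepts that conditioning for the other scales, so the addition would be consistent with them. Omitting it does not make the unadjusted contrast wrong.

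Fourth, imbalance would be partly visible anyway, because baseline values are reported with their follow-up measures (SAP 8.3). That shows a gap but does not adjust for it.

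**Conclusion.** This is an inexpensive improvement to a secondary analysis. The text is clear: the baseline term is dropped without a substitute, the responder comparison is unadjusted, and the other efficacy models use baseline scores that could fill the gap. The gain is negligible at rho 0.1, modest at 0.3 and worthwhile at 0.5. Neither rho nor the entry-severity gap can be obtained from the documents.

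A reader might also infer a loss of power. With an assumed 0.4 SD difference and 100 per group, power would be 0.807 unadjusted, 0.843 adjusted at rho 0.3 and 0.904 at rho 0.5. The trial sets no power target and does not give these inputs, so the figures illustrate precision and do not show a shortfall.

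**What to change.** - **SAP 9.1.1:** in the CGI-I model, replace the deleted term with one P306 baseline severity score, BDI-II total or SDS total, and its visit interaction. Name the score in advance.
- **SAP 9.1.2:** add a responder risk difference with 95% CI, standardised from a logistic model with group, that baseline score and sex. Keep the Z-test as the unadjusted display.
- **Interpretation:** state that the adjusted contrast is conditional on severity at P306 entry, as it already is for SDS, PROMIS and BDI-II.

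The cost is SAP wording and minor programming, with no new data collection. A patient without the chosen baseline score leaves the adjusted model unless a simple baseline fill is specified. For SDS, SAP 7.2.2 sets the total to missing when an item is blank, apart from the work/school item when the patient has not worked or studied for reasons unrelated to PTSD. A few parameters are added, and the return is small if the correlation is low.
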